#### *Rationale for dosing periods*

To ensure safe rollover of those subjects previously on placebo and minimize the risks of potential unblinding all eligible subjects will receive pimavanserin “low dose” for the first two weeks of the study. Subjects who were on “**CCI** dose” during the antecedent double-blind study will likely experience **CCI** efficacy during this period, due to the long half-life of pimavanserin, and having achieved steady state by the end of the antecedent double-blind study. At the Week 2 visit, the dose may be increased to pimavanserin “high dose”, based on the Investigator’s assessment of clinical response.

After the Week 2 visit, and up to and including the Week 20 visit, dose adjustments, either increases or decreases, may be made at any clinic visit (scheduled or unscheduled), based on the Investigator’s assessment of clinical response and tolerability.

No further dose adjustments are allowed after the Week 20 visit.

## **1.5 Benefit/Risk Assessment**

### **1.5.1 Known Potential Risks**

The Prescribing Information for NUPLAZID® (pimavanserin) tablets and capsules for oral use ([Acadia Pharmaceuticals Inc. 2020](#)) includes the following Boxed Warning:

**“WARNING: INCREASED MORTALITY IN ELDERLY PATIENTS WITH DEMENTIA-RELATED PSYCHOSIS”**

The increased mortality warning in elderly patients with dementia-related psychosis is based on information regarding antipsychotic drugs in general, rather than specific pimavanserin data.

The Warnings and Precautions section of the Prescribing Information for pimavanserin also includes information about QT interval on ECG (QT) interval prolongation. Pimavanserin prolongs the QT interval. The use of pimavanserin should be avoided in patients with known QT prolongation or in combination with other drugs known to prolong QT interval including Class 1A antiarrhythmics (e.g., quinidine, procainamide) or Class 3 antiarrhythmics (e.g., amiodarone, sotalol), certain antipsychotic medications (e.g., ziprasidone, chlorpromazine, thioridazine), and certain antibiotics (e.g., gatifloxacin, moxifloxacin). Pimavanserin should also be avoided in patients with a history of cardiac arrhythmias, as well as other circumstances that may increase the risk of the occurrence of torsade de pointes and/or sudden death, including

symptomatic bradycardia, hypokalemia or hypomagnesemia, and the presence of congenital prolongation of the QT interval.

NUPLAZID is contraindicated in patients with a history of a hypersensitivity reaction to pimavanserin or any of its components. Rash, urticaria, reactions consistent with angioedema (e.g., tongue swelling, circumoral edema, throat tightness, and dyspnea) have been reported. In addition, adverse reactions of somnolence, falls, agitation, and aggression have been reported during postapproval use of NUPLAZID.

Pimavanserin has not yet been studied as monotherapy in children and adolescents therefore no data are available on specific risks in this population. In adolescents treated with pimavanserin in combination with other psychotropics, pimavanserin dose-related QTc prolongation, and a trend for higher exposure with decreasing age and decreasing body weight, have been observed.

### **1.5.2 Known Potential Benefits**

Pimavanserin has not been studied in children and adolescents with ASD, thus there are no known benefits. It has shown antipsychotic properties in the indications of PDP, and is currently being evaluated as adjunctive treatment in adults with negative symptoms of schizophrenia. Based on the mechanism of action of pimavanserin, potential benefits may include its clinical utility in the treatment of irritability and other symptoms of ASD. This is particularly the case with subjects previously randomized to placebo. Subjects may benefit from the increased medical care and attention for the study duration.

A detailed summary of the potential risks and benefits is available in the pimavanserin Investigator's Brochure.

## **2 STUDY OBJECTIVES AND ENDPOINTS**

### **2.1 Primary Objective**

- To evaluate the long-term safety and tolerability of pimavanserin after 52 weeks of treatment in children and adolescents with ASD

#### **2.1.1 Primary Endpoints**

- Treatment-emergent adverse events (TEAEs)

Safety will also be evaluated by analyses of the following:

- Vital signs
- Weight and body mass index (BMI)
- 12-lead electrocardiograms (ECGs)
- Physical examination results

- Clinical laboratory tests (including urinalysis) and hormonal assessments
- Columbia–Suicide Severity Rating Scale (C-SSRS)
- Extrapyramidal Symptom Rating Scale-Abbreviated (ESRS-A)

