#### 6.4.4 Laboratory Evaluations

Clinical laboratory sample collection (including HbA1c) is encouraged, but not required, to be completed under fasting conditions. The laboratory evaluations will include, but are not limited to, the following:

- Clinical chemistry serum tests
  - Sodium (Na), potassium (K), carbon dioxide (CO2), chloride (Cl), phosphorus (P), calcium (Ca), blood urea nitrogen (BUN), creatinine (CR), glucose, albumin (ALB), total protein
    - *In Italy only:* [REDACTED]  
[REDACTED]  
[REDACTED]  
[REDACTED]  
[REDACTED]  
[REDACTED]  
[REDACTED]  
[REDACTED]
  - Alanine aminotransferase (ALT), aspartate aminotransferase (AST), gamma-glutamyl transpeptidase (GGT), alkaline phosphatase (ALP), total bilirubin (TBIL), lactate dehydrogenase (LDH)
  - Lipid panel

- Total cholesterol, high-density lipoprotein (HDL)-cholesterol, triglycerides, low-density lipoprotein (LDL)-cholesterol, cholesterol/HDL ratio, non-HDL cholesterol
- HbA1c
- Prolactin
  - Prolactin CCI  
[REDACTED] Results will be monitored CCI  
[REDACTED]
- Creatine kinase (CK)/creatine phosphokinase (CPK)
- Pregnancy test
  - A urine pregnancy test should be performed at all designated visits ([Table 6–1](#)) for women of child-bearing potential. If positive, the result will be confirmed with a serum pregnancy test.
    - If urine cannot be obtained in women of childbearing potential, a serum pregnancy test should be done in its place
- Hematology tests
  - Complete blood count (CBC) including:
    - White blood cell (WBC) count
    - Complete differential (relative and absolute)
    - Hematocrit (Hct), hemoglobin, red blood cells (RBC), platelets
    - Reticulocyte count
- Urinalysis
  - Blood, RBCs, WBCs, protein, glucose, ketones, specific gravity, pH
  - Reasonable efforts should be made to collect a urine sample from all subjects. When collection of a urine sample proves impractical or impossible (e.g., because the subject is incontinent or unable to cooperate), failure to collect a urine sample should be recorded in the subject's eCRF, and will not be considered a protocol deviation.
- Urine toxicology screen

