## Appendix C Criteria for Identifying Potentially Clinically Important Laboratory Values

Analyte	Conventional Unit	Low PCI Criteria	High PCI Criteria
Hematology (whole blood)			
Hemoglobin (Male)	g/dL	<11	>17
Hemoglobin (Female)	g/dL	<10	>17
Hematocrit (Both)	%	<30	>50
Leukocyte (White Blood Cell Count)	× 10  /uL	≤2.8	≥15
Neutrophils	× 10  /uL	≤1.5	No upper limit
Eosinophils	%	≥10%	No lower limit
Platelet Count	× 10  /uL	≤75	≥700
Chemistry (serum or plasma)			
ALT (SGPT)	U/L	No lower limit	≥3 × ULN
AST (SGOT)	U/L	No lower limit	≥3 × ULN
Gamma-Glutamyl Transferase (GGT)	U/L	No lower limit	≥3 ULN
Lactate Dehydrogenase (LDH)	U/L	No lower limit	≥3 × ULN
Alkaline Phosphatase	U/L	No lower limit	≥3 × ULN
Total Bilirubin	mg/dL	No lower limit	≥1.5 ULN
CPK	mg/dL	No lower limit	≥3 ULN
BUN	mg/dL	No lower limit	≥30.0
Serum Creatinine	mg/dL	Not Applicable	>1.5 ULN
Sodium	mEq/L	≤125	≥155
Potassium	mEq/L	≤3.0	≥5.5
Calcium, total	mg/dL	<8.0	>11.0
Chloride	mEq/L	≤85	≥120
Phosphorous, inorganic	mg/dL	≤1.0 mg/dL	≥4.5 mg/dL
Magnesium	mEq/L	≤0.7 mEq/L	≥5.0 mEq/L
Uric acid	mg/dL	No lower limit	≥8.5
Albumin	g/dL	≤2.6	≥6.0
Total Protein	g/dL	≤5.0	≥10.0
Glucose (random)	mg/dL	≤45.1	≥115.0
Hb1Ac	%	No lower limit	≥7%
Total Cholesterol, Fasting	mg/dL	No lower limit	≥240 mg/dL
Urinalysis			
Blood (occult blood)		Not Applicable	≥ Moderate
Protein	mg/dL	Not Applicable	≥100 mg/dL
Glucose	mg/dL	Not Applicable	≥500 mg/dL

Abbreviations: ALT (SGPT)=alanine aminotransferase (serum glutamic-pyruvic transaminase);

AST (SGOT)=aspartate aminotransferase (serum glutamic-oxaloacetic transaminase); BUN=blood urea nitrogen; CPK=creatine phosphokinase; HbA1c=glycosylated hemoglobin; PCI=potentially clinically important; ULN=upper limit of normal.

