14.2 Clinical Laboratory Variables

Clinical laboratory tests are performed at Baseline, Week 2, Week 6, Week 12, week 20, Week 28, Week 36, Week 44 and Week 52 visits.

Due to COVID-19 disruptions it is possible that some test results may be collected from a local laboratory. Local laboratory results and the associated normal ranges will be converted to SI units; the local laboratory results, in SI units, will then be normalized to central lab ranges to be included in summary data analysis together with the central laboratory results. The normalization will be performed using the following scale transformation equation:

$$s = L_s + (x - L_x) \frac{U_s - L_s}{U_x - L_x}$$

where s is the normalized individual laboratory value to be used for summary; x is the original value from the local lab; L_x and U_x are the lower and upper limits from the local lab; L_s and U_s are the lower and upper limits from the central lab.

For labs with only a single upper (or lower) limit, the following scale transformation equation will be used:

$$s = x \frac{U_s}{U_x}$$

where s is the normalized individual laboratory value to be used for summary; x is the original value from the local lab; U_s is the upper (or lower) limit from the central lab; U_x is the upper (or lower) limit from the local laboratory. Local laboratory results and normalized results will be included in data listings. Only central lab and normalized local lab results will be used for summary of change from baseline, shift, and potentially clinically important (PCI) analyses.

Clinical laboratory tests include the following:

- Clinical chemistry serum tests
 - Sodium (Na), potassium (K), carbon dioxide (CO₂), chloride (Cl), phosphorus (P), calcium (Ca), blood urea nitrogen (BUN), creatinine (CR), glucose, albumin (ALB), total protein

- Alanine aminotransferase (ALT), aspartate aminotransferase (AST), gamma-glutamyl transpeptidase (GGT), alkaline phosphatase (ALP), total bilirubin (TBIL), lactate dehydrogenase (LDH)
- Lipid panel
 - Total cholesterol, high-density lipoprotein (HDL)-cholesterol, triglycerides, low-density lipoprotein (LDL)-cholesterol, cholesterol/HDL ratio, non-HDL cholesterol
- HbA_{1c}
- Prolactin
 - Prolactin results should be blinded to the Investigator and the Sponsor at Baseline. Results will be monitored by an independent Medical Monitor from the Clinical Research Organization (CRO).
- Creatine kinase (CK)/creatine phosphokinase (CPK)
- Pregnancy test

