14.2.1 Analysis of Clinical Laboratory Variables

14.2.1.1 Observed Values and Change from Baseline

All laboratory test results will be provided in the listings. The listings will include date and study day of collection. All units will be displayed in Système International [SI] units. Out of range values will be flagged in the data listings (e.g. 'L' or 'H').

Clinical laboratory values for hematology, chemistry and urinalysis will be summarized using descriptive statistics at Baseline, Week 3 and Week 6. The change from Baseline values will also be summarized at Week 3 and Week 6. The overall minimum and maximum post-baseline observed and change from Baseline values will also be summarized. For hemoglobin, hematocrit and uric acid, the above summaries will be presented for each gender as well as for both genders combined. For urinalysis with categorical results (blood, protein, glucose, and ketones), the number and percentage of subjects will be tabulated by category at Baseline, Week 3 and Week 6, with the denominator being the number of subjects with non-missing values for the given parameter, visit and cohort.

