14.2.1.2 Shift Tables

Laboratory values will be summarized in shift tables to determine the number and percentage of subjects with values classified as below (low), within (normal), and above (high) normal ranges at scheduled post-baseline minimum relative to the same classification at the Baseline visit. The shifts from Baseline to overall post-Baseline minimum and overall post-Baseline maximum will also be presented, only for the open-label treatment period. For the by-visit shift summary, the denominator is the number of subjects with non-missing values at Baseline and the given visit for the given parameter and cohort. For the shift to the overall post-baseline minimum or maximum, the denominator is the number of subjects with non-missing Baseline and at least one post-baseline value for the given parameter and cohort. For hemoglobin, hematocrit and uric acid, the shift summaries will be presented for each gender as well as for both genders combined.

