14.2.1.3 Potentially Clinically Important (PCI) Laboratory Values

The number and percentage of subjects with PCI laboratory values at scheduled post-Baseline visits and overall post-Baseline (for the open-label treatment period) will be summarized by Baseline status (all and within normal range) for selected parameters. PCI criteria are listed in [Table 3](#) and [Table 4](#). For the overall post-baseline summaries of PCI values, all post-baseline values will be considered, including unscheduled and out of window values. Subjects with multiple PCI values for a given parameter will be counted only once for that parameter. For the by-visit summary, the numerator for the percentage is the number of subjects with a post-baseline PCI value for the given parameter, visit and cohort, and the denominator is the number of subjects with non-missing values for the given parameter, visit and cohort. For the overall post-baseline summary, the numerator for the percentage is the number of subjects with at least one post-baseline PCI laboratory value for the given parameter and cohort, and the denominator is the number of subjects with at least one post-baseline laboratory value for the given parameter and cohort. For hemoglobin, hematocrit and uric acid, the count and percentage of subjects with PCI values will be presented for each gender as well as for both genders combined. A listing of all PCI values in study -070 will be provided. This listing will include all observations from study -070 for those subjects and parameters for which at least one PCI value (including Baseline) was observed.

Table 3 Criteria for Potentially Clinically Important Laboratory Values – Hematology and Chemistry

Analyte	Conventional Unit	Low PCI Criteria	High PCI Criteria	SI Unit	Low PCI Criteria	High PCI Criteria
Hematology (whole blood)						
Hemoglobin (male)	g/dL	<11	>17	g/L	<110	>170
Hemoglobin (female)	g/dL	<10	>17	g/L	<100	>170
Hematocrit	%	<30	>50	L/L	<0.3	>0.50
Leukocyte (White Blood Cell Count)	x 10 ³ /uL	≤2.8	≥15	x 10 ⁹ /L	≤2.8	≥15
Neutrophils	x 10 ³ /uL	≤1.5	No upper limit	x 10 ⁹ /L	≤1.5	No upper limit
Eosinophils	%	No lower limit	≥10	L/L	No lower limit	≥10
Platelet Count	x 10 ³ /uL	≤75	≥700	10 ⁹ /L	≤75	≥700
Chemistry (serum or plasma)						
ALT (SGPT)	U/L	No lower limit	≥3 X ULN	U/L	No lower limit	≥3 X ULN
AST (SGOT)	U/L	No lower limit	≥3 X ULN	U/L	No lower limit	≥3 X ULN
Total Bilirubin	mg/dL	No lower limit	≥1.5 ULN	umol/L	No lower limit	≥1.5 ULN

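### Prolactin, the only hormone on the listed panels apart from the pregnancy test, is left out of the SAP's by-gender laboratory summaries, while uric acid, which is on neither listed panel, is included.

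*Protocol*

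**What the plan says.** Protocol 2.1.1 makes TEAEs the primary endpoint and adds further safety measures, among them "Clinical laboratory tests (including urinalysis) and hormonal assessments".

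Protocol 6.4.4 and SAP 14.2 list the same laboratory tests. Prolactin is on both lists. The only other hormone test is hCG, for pregnancy. SAP 14.2 adds a handling rule for prolactin: "Prolactin results should be blinded to the Investigator and the Sponsor at Baseline", with monitoring by an independent Medical Monitor.

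The SAP separates the sexes for a fixed set of analytes. SAP 14.2.1.1 says: "For hemoglobin, hematocrit and uric acid, the above summaries will be presented for each gender as well as for both genders combined". SAP 14.2.1.2 repeats the set for shifts: "For hemoglobin, hematocrit and uric acid, the shift summaries will be presented for each gender as well as for both genders combined". SAP 14.2.1.3 names the same three for potentially clinically important (PCI) values. Prolactin is in none of the three.

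Uric acid is in all three, and has a PCI row in Protocol Appendix C and SAP Table 3, but it is on neither laboratory list. Magnesium also has PCI rows and is on neither list.

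**The concern.** When a safety measure is named in the protocol, the reader expects the SAP to say how it will be reported. Here the hormonal measure comes down to one analyte, and that analyte gets only the default treatment for chemistry. The SAP already has a format for reporting laboratory results by sex. It gives one of the three places to an analyte that the listed panels do not include, and none to the hormone.

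The subjects are boys and girls aged 5 through 17 at entry to the antecedent study. If a change in prolactin occurred mainly in one sex, the pooled mean change would understate it. Nothing else in the SAP would recover it: the sex subgroup in SAP 12.5 applies only to ABC-I change. What is at stake is how clearly a secondary safety measure can be read, not the primary result.

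**Working it through.** The plan states no figure on this point, so there is none to reproduce. The check compares lists and adds one line of arithmetic.

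**1. Which analytes appear where**

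| Analyte | Listed panel (Protocol 6.4.4, SAP 14.2) | By-gender set (SAP 14.2.1.1–14.2.1.3) | PCI row (Appendix C, SAP Table 3) |
|---|---|---|---|
| Hemoglobin | yes | yes | yes, limits by sex |
| Hematocrit | yes | yes | yes, one set of limits |
| Uric acid | no | yes | yes |
| Magnesium | no | no | yes |
| Prolactin | yes | no | no |

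Two of the three by-gender analytes are on the panel and one is not. No sentence says that prolactin is pooled over the sexes; that follows from its absence from the by-gender set.

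**2. What pooling does to a mean change**

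Let p be the proportion of girls, and let D_g and D_b be the mean changes in girls and boys. Then:

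pooled mean change = p × D_g + (1 − p) × D_b

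If the change is confined to girls, D_b = 0 and the pooled change is p × D_g. The documents give no sex mix, so p is assumed. The counts use the 193 subjects of Protocol 9.3.

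| p (assumed) | Girls among 193 | Part of D_g seen in the pooled mean |
|---|---|---|
| 0.15 | 193 × 0.15 ≈ 29 | 15% |
| 0.20 | 193 × 0.20 ≈ 39 | 20% |
| 0.25 | 193 × 0.25 ≈ 48 | 25% |

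This holds for the absolute change whatever the Baseline levels are. A percentage rise does not behave so simply. With p = 0.20, a 50% rise in girls and equal Baseline means, the pooled rise is 0.20 × 50% = 10%. If girls start at twice the boys' level (boys = 1, girls = 2), the pooled Baseline is 0.8 × 1 + 0.2 × 2 = 1.2. The pooled increase is 0.2 × 1 = 0.2, and 0.2/1.2 = 16.7%. The conclusion is therefore stated in absolute terms only.

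**3. When the data exist**

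SAP 14.2.1.1 puts the laboratory summaries at Baseline, Week 3 and Week 6. Protocol Table 6–1 schedules chemistry at Baseline and Weeks 12, 28, 44 and 52 (or early termination). There is no Week 3 visit, and only a urine pregnancy test is scheduled at Week 6. I take prolactin to be drawn with chemistry, because Table 6–1 has no separate line for it. As written, a by-visit prolactin table, by sex or not, would hold no scheduled post-baseline result. At most an early-termination or unscheduled draw could fall in the Week 6 window. The opening sentence of SAP 14.2 lists every clinic visit and so disagrees with both.

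**The case against.** The strongest reply is that prolactin is already well covered. As a listed chemistry test it receives descriptive summaries, overall post-baseline minimum and maximum, and listings with out-of-range flags (SAP 14.2.1.1), plus low/normal/high shifts (SAP 14.2.1.2). The shift table counts individual subjects who move out of range, so the dilution of a mean does not apply to it. An independent Medical Monitor follows prolactin, the DSMB reviews safety laboratory data (Protocol 9.7, SAP 17), and an abnormal laboratory finding can be an adverse event (Protocol 7.1.1). All of this stands. It limits the point to how results are presented; it does not give a by-sex reading.

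Several stronger readings are tempting, and the documents do not support them:

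- **The uric acid cells will be empty.** Protocol 6.4.4 says "The laboratory evaluations will include, but are not limited to, the following", and part of its text is blacked out. What can be said is that uric acid is on neither listed panel.
- **Uric acid was written where prolactin was meant.** Uric acid has PCI rows in both documents. An analyte left off the panel list, or leftover text, is just as plausible.
- **The missing PCI limit is an error.** PCI values "will be summarized by Baseline status (all and within normal range) for selected parameters", and other panel analytes, such as HDL, LDL, carbon dioxide and reticulocytes, have no limit either.
- **Blinding at Baseline shows that prolactin was seen as a special risk.** Baseline is the end-of-treatment visit of the double-blind study, so the rule may equally protect that study's blind.

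That prolactin differs by sex and puberty is not stated in the documents, and neither is whether the laboratory's normal ranges are sex-specific. The point does not depend on either.

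**Conclusion.** The point holds as a low-cost improvement in safety reporting. The protocol names hormonal assessments, prolactin is the only listed analyte that answers to that name apart from hCG, and the SAP does not present it by gender although it does so for three other analytes. A mean shift confined to girls would appear in the pooled mean change at 15% to 25% of its absolute size if girls are 15% to 25% of subjects. That range is assumed. So is a zero change in boys, which is what a shift confined to girls means.

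A reader might infer that the hormonal measure goes unanalysed or that the primary analysis is weakened. Neither follows: prolactin has the coverage described above, and the TEAE endpoint is untouched. The mismatch of uric acid and magnesium with the listed panel is a separate matter of consistency.

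**What to change.** - In SAP 14.2.1.1, add prolactin to the analytes presented for each gender and combined, for observed values, change from Baseline, and overall minimum and maximum. Do the same for shifts in SAP 14.2.1.2.
- Tabulate at Baseline and Weeks 12, 28, 44 and 52, in place of Weeks 3 and 6. Without this correction the added tables would hold no scheduled post-baseline results. Bring the opening sentence of SAP 14.2 into line.
- State that hormonal assessments means prolactin, or list any other hormone intended.
- Reconcile uric acid (by-gender text and PCI rows) and magnesium (PCI rows) with the listed panel in both documents. Either confirm that they are assayed and list them, or delete them.
- A prolactin PCI limit is optional and is for the sponsor to decide. If one is set, add prolactin to the by-gender sentence in SAP 14.2.1.3.

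The cost is SAP wording and a few added table rows, with no new data collection. The table specifications are in a separate document that was not available, so the programming effort cannot be judged. The drawback is small female cells: about 29 to 48 girls under the assumed mix. If the tables are also split by the three double-blind groups in equal parts (a further assumption), that is about 29/3 ≈ 10 to 48/3 = 16 per group. This is acceptable in a purely descriptive analysis if the counts are shown.
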